8.7.1 Urine Albumin-Creatinine Ratio and Urine Protein-Creatinine Ratio

A urine sample for urine albumin-creatinine ratio and urine protein-creatinine ratio will be collected at visits specified in the Schedule of Procedures (Appendix A). Samples should be collected while the participant is fasting (a minimum of 8 hours).

8.7.2 Aldosterone and High Sensitivity C-Reactive Protein

A plasma sample for aldosterone and high sensitivity C-reactive protein will be collected at visits specified in the Schedule of Procedures (Appendix A). Samples should be collected while the participant is fasting (a minimum of 8 hours).

8.7.3 Efficacy Endpoint Laboratory Assessments

Although laboratory values that are part of the efficacy endpoints will not be provided to the sites, the Investigator will be notified of critical high LDL-C values as follows:

- If **before Day 84**, when the LDL-C values of a participant are >200 mg/dL (>5.18 mmol/L) **AND** exhibit a $>50\%$ increase compared to Baseline; or
- If **after Day 84**, when the LDL-C values of a participant are >200 mg/dL (>5.18 mmol/L) **OR** exhibit a $>50\%$ increase compared to Baseline.

These critical high values will need to be confirmed by a repeat measurement (new fasting blood sample). The Investigator should be encouraged to consult with the Medical Monitor. Investigators

and the blinded study team will be informed that random sham alerts will also be sent to sites, in order to maintain the study blind.

8.7.4 Managing Abnormal and Critical Laboratory Values

Any laboratory test result abnormality that fulfills the criteria for an SAE will be reported as such on the appropriate AE and SAE eCRF. Any treatment-emergent abnormal laboratory result that is clinically significant, ie, meets 1 or more of the following criteria, will be recorded as a single diagnosis on the AE eCRF:

- Is accompanied by clinical symptoms;
- Leads to a change in study drug (eg, study drug interruption or permanent discontinuation); and/or
- Requires a change in concomitant therapy or a medical intervention (eg, the addition of, interruption of, or discontinuation of, or any other change in a concomitant medication, therapy, or treatment).

These criteria apply to any protocol and non-protocol-specified safety and/or efficacy laboratory results from tests performed after the first dose of study drug that meet clinical significance criteria. These criteria do not apply to any abnormal laboratory test results which fall outside the laboratory reference range, but which do not meet clinical significance criteria (these will be analyzed and reported as laboratory abnormalities) or those which are a result of an AE or an endpoint which has already been reported.

The Investigator is responsible for reviewing laboratory test results and determining whether an abnormal value in an individual participant represents a clinically significant change from the participant's Baseline values. In general, laboratory abnormalities without clinical significance should not be recorded as AEs. Where applicable, the clinical sequelae, not the laboratory abnormality, should be recorded as the AE.

Critical laboratory values are values that may warrant medical intervention to avoid possible harm to a participant. Critical laboratory values will be defined in the Laboratory Manual for the study, and the Medical Monitor and Investigator will be notified of the occurrence of a critical laboratory value (critical high or critical low) by a special annotation (flag) in the laboratory reports provided to the sites.

If LDL-C values are confirmed critically high (see [Section 8.7.3](#)), OR if TG levels exceed 500 mg/dL (5.65 mmol/L), the Investigator may need to take appropriate medical action, which could include the following: reinforce/intensify therapeutic lifestyle changes (including diet and physical activity), increase the dose of the present statin therapy, add ezetimibe, or prescribe a more potent lipid-modifying therapy to lower LDL-C. The Investigator should use the best clinical judgment for each participant.

8.8 Vital Signs

Vital signs (consisting of heart rate and blood pressure) will be measured in triplicate prior to study drug administration at applicable visits (see [Appendix A](#)). On Day 1 (Visit 2), blood pressure will be measured prior to Randomization. When available, an automated blood pressure device is recommended for collection of blood pressure and the result should be recorded to the nearest mmHg.

Vital signs will be measured using the following standardized procedures:

- Participants should not exercise, smoke, or consume caffeinated beverages or food 30 minutes prior to assessment of vital signs; and
- Vital signs should be obtained prior to ECG recordings.

8.8.1 Blood Pressure Monitoring

Blood pressure specifically will be measured using the following standardized procedures:

- Participants should be seated for at least 5 minutes in the examination room with the back supported, feet flat on the floor, and the measurement arm supported so that the midpoint of the manometer cuff is at heart level;
- An appropriately sized cuff should be used with the bladder centered over the brachial artery;
- The cuff size and arm used for the measurement should be recorded; the same arm should be used for all readings;
- Three seated blood pressure measurements (each measurement 1 to 2 minutes apart) should be obtained using the same arm at each site visit. Mean seated blood pressure is defined as the average of 3 seated blood pressure measurements at a single site visit; and
- If the lowest and highest blood pressure measurements are >15 mmHg apart, additional readings should be performed.

Blood pressure readings, both systolic and diastolic, will be evaluated over time by the independent DSMB, who will monitor unblinded safety data during the study. Changes in blood pressure, as well as heart rate, will be compared between treatment groups with respect to mean and median values over time using both actual values and absolute changes from Baseline. In addition, treatment groups will be compared with respect to the incidence of hypertensive status and other vital sign abnormalities as defined in the Statistical Analysis Plan (SAP).

8.9 Electrocardiograms

A single 12-lead ECG will be performed in the supine position after 10 minutes of rest at visits specified in [Appendix A](#). ECGs are to be assessed for clinical significance by a qualified medical designee at the study site.

8.10 Physical Examinations

Physical examinations will be completed at visits specified in [Appendix A](#). The physical examination should comprise a focused examination, which includes general, respiratory, cardiovascular, abdominal, and extremities evaluations; ophthalmological examination; and recording of weight and height. Height will be measured at Screening only and used to calculate body mass index.

9 STATISTICS

9.1 Analysis Populations

The Intent-to-Treat (ITT) Population will include all participants who are randomized into the study. Treatment classification will be based on the randomized treatment.

The Full Analysis Set (FAS) will include all participants who are randomized into the study, take any study drug, and have at least 1 post-treatment lipid data assessment. Treatment classification will be based on the randomized treatment.

The Modified ITT (mITT) Population will include all randomized participants who receive at least 1 dose of any study drug and have data for both the Day 1 and Day 84 LDL-C assessments. Treatment classification will be based on the randomized treatment.

The Per-Protocol (PP) Population will include all participants in the mITT Population who did not experience a major protocol deviation that potentially impacted the primary efficacy endpoint. The PP Population, along with the reason for exclusion, will be finalized prior to study unblinding.

The Safety Population will include all participants who receive at least 1 dose of any study drug. Treatment classification will be based on the actual treatment received. The Safety Population will be the primary population used for the safety analyses.

9.2 Statistical Methods

An SAP will be finalized before database lock. Any changes to the methods described in the SAP will be described and justified as needed in the final Clinical Study Report. All study-collected data will be summarized by treatment group using descriptive statistics, graphs, and/or raw data listings. Descriptive statistics for continuous variables will include number of participants, mean, standard deviation, median, minimum, and maximum values. Analyses of categorical variables will include frequency and percentage.

Unless otherwise stated, Baseline values will be the last non-missing measurements taken prior to the participant receiving study drug.

9.2.1 Analysis of Efficacy

9.2.1.1 Primary efficacy analysis

The ITT Population will be the primary population for the efficacy analysis. Efficacy will also be analyzed using the FAS, mITT Population, and PP Population as supportive analyses.

The primary efficacy endpoint is the percent change from Baseline to Day 84 in fasting LDL-C in the obicetrapib group compared to the placebo group. The primary endpoint will be analyzed using an analysis of covariance (ANCOVA) model with a fixed effect for the treatment group and covariate of Baseline LDL-C. The least squares (LS) mean, standard errors, and 2-sided 95% confidence intervals for each treatment group and for the mean difference compared to placebo will be obtained. Model diagnostics for the ANCOVA model will be computed that include assessments for homogeneity of variance, normality of the residuals, and residual outliers. If substantial deviations from the model assumptions are observed, then supportive analyses, such as an ANCOVA model assuming unequal variances or non-parametric assessments, will be considered.

The primary estimand will correspond to a treatment policy estimand. The target population will comprise participants who are randomized into the study. The primary summary measure to access the treatment effect will be the LS mean difference for the primary endpoint between obicetrapib and placebo based on the ANCOVA methodology. The primary estimand will be addressed using the in-study observation period (ie, including data collected post-treatment discontinuation or post-prohibited medication use).

Missing data will be imputed for the primary efficacy analysis based on a pattern mixture model that uses a multiple imputation technique analyzed with ANCOVA with pre-specified fixed factors and covariates. If appropriate, based on the number of retrieved dropouts, missing measurements of non-retrieved dropouts will be modeled by known measurements from retrieved dropouts (ie, participants who remain in the study after treatment discontinuation) in the same treatment group. The imputation model will be further clarified in the SAP.

Additional sensitivity analyses may be carried out under secondary estimands and/or various assumptions for missing data. Full details will be provided in the SAP.

9.2.1.2 Secondary and exploratory efficacy analyses

In order to control the Type I error rate, a fixed sequential testing procedure will be implemented. In a hierarchical step-down manner, the primary endpoint will be tested first, followed by the secondary efficacy endpoints in a pre-specified order. The pre-specified order of the hypothesis testing for the secondary endpoints will be described in the SAP. No adjustment for multiple comparisons will be made for the exploratory efficacy endpoints.

Continuous secondary and exploratory efficacy endpoints will be analyzed using similar methods as in the primary efficacy analysis. For the binary exploratory efficacy endpoints, a logistic regression analysis will be performed with model covariates of treatment group and Baseline LDL-C. Odds ratio and 95% confidence interval for the odds ratio will be obtained. Nominal p-values will be provided when applicable. Descriptive and graphical summaries by treatment group will also be presented.

Full details of the models and analyses to be performed will be provided in the SAP.

9.2.2 Analysis of Safety

The Safety Population will be the primary population for the safety analysis. All safety endpoints will be summarized descriptively. No statistical inference will be applied to the safety endpoints.

AEs will be categorized by primary system organ class and preferred term as coded using the Medical Dictionary for Regulatory Activities category designations. Summaries of AEs, including the number and percentage of participants who experience an AE, will be provided.

Laboratory values will be summarized descriptively, including the change from Baseline, by treatment group, and overall. In addition, shift tables will be presented to describe the change in laboratory parameter values at post-Baseline visits using normal range categories (low, normal, and high).

9.2.2.1 Analysis of ESIs

Liver-associated enzymes and total bilirubin will be summarized by the value and change from Baseline in the value, by treatment group and visit. In addition, the number and percent of participants with abnormal values for ALT, AST, and total bilirubin will be summarized. These

summaries of participants with abnormal values will be performed overall; by normal Baseline; and by abnormal Baseline for ALT, AST, and total bilirubin individually. Hy's Law criteria ($>3 \times \text{ULN}$ for either ALT or AST, with accompanying total bilirubin $>2 \times \text{ULN}$) will also be applied to the data. Any potential Hy's Law cases will be listed separately.

CK levels will be summarized by the value and change from Baseline in value, by treatment group and visit. In addition, the number and percent of participants with abnormal CK values will be summarized. These summaries of participants with abnormal CK values will be performed overall, by normal Baseline CK, and by abnormal Baseline CK. Values of CK from Baseline to EOT will be summarized by treatment group and by Baseline eGFR category.

Cases of NODM will be recorded and summarized using the appropriate system organ class. These events will be summarized by severity and relationship to study drug for each treatment group. Fasting plasma glucose and HbA1c will be monitored as specified in [Appendix A](#).

Baseline eGFR will be summarized by treatment group for actual value and for Baseline eGFR categories. Shift tables of eGFR category from Baseline to EOT will be provided by treatment group. Shift tables of urine albumin-creatinine ratio and urine protein-creatinine ratio from Baseline to EOT will be provided by treatment group. Muscle-related abnormalities will be summarized by treatment group and by Baseline eGFR category.

The number and percentage of participants receiving antihypertensive medication(s) treatment at Baseline with changes to antihypertensive medication(s) due to changes in blood pressure will be summarized by treatment group.

Cases of macular degeneration will be recorded and summarized using the appropriate system organ class. These events will be summarized by severity and relationship to study drug for each treatment group.

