8.1.4 Events of Special Interest

ESIs will be monitored over time by the independent DSMB, as described in the DSMB charter, regardless of whether these events were reported as AEs. Any events that qualify as an AE or SAE will be reported accordingly (see [Sections 8.1, 8.2, and 8.3](#)).

ESIs will include the following hepatic abnormalities, muscle-related abnormalities, new-onset diabetes mellitus (NODM) and/or hyperglycemia, renal abnormalities, changes to antihypertensive medication(s) due to changes in blood pressure, and ophthalmic events (ie, macular degeneration), described as follows:

- AST or ALT $>3 \times$ ULN;
- Bilirubin $>2 \times$ ULN;
- CK $>5 \times$ ULN;
- NODM or worsening of glycemic control;

Note: NODM is defined by 1 or more of the following criteria, based upon information from AE, medication, and laboratory data:

- AE indicating new type 1 or type 2 diabetes;
- Initiation of anti-diabetes medication with confirmation of the diagnosis of diabetes by blinded external review by experts in diabetology;
- HbA1c $\geq 6.5\%$ (≥ 0.065 hemoglobin fraction); and/or
- Two consecutive values of fasting plasma glucose that are ≥ 126 mg/dL (≥ 7.0 mmol/L).

Note: Worsening of glycemic control will be defined as an HbA1c increase from Baseline $>0.5\%$ (>0.005 hemoglobin fraction) and/or a new concomitant medication or increase in current antidiabetic therapy in a participant with a Baseline HbA1c $\geq 6.5\%$ (≥ 0.065 hemoglobin fraction).

- A >25% decrease in eGFR from Baseline or an eGFR <30 mL/min/1.73 m², calculated using the Chronic Kidney Disease Epidemiology Collaboration equation, and/or an increase in serum creatinine of ≥ 0.3 mg/dL (≥ 26.5 μ mol/L) from Baseline;
- Changes to antihypertensive medication(s) due to changes in blood pressure in those participants receiving antihypertensive medication(s) treatment at Baseline; and
- Macular degeneration.

These ESIs will be monitored through review of the AE and laboratory database.

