3.5 Safety Assessment

Safety Population will be the primary population for the safety analyses. All safety endpoints will be summarized descriptively by treatment group and overall. No statistical inference will be applied to the safety endpoints.

3.5.1 *Adverse Events (AEs)*

AEs will be categorized by primary system organ class and preferred term as coded using the current MedDRA version category designation.

An overview of treatment-emergent AEs (TEAEs) will be provided including counts and percentages of participants with the following:

- Any TEAEs (overall and by maximum severity)
- Any TEAEs (non-serious)
- Any study drug related TEAEs (overall and by maximum severity)
- Any TEAEs leading to discontinuation of study drug
- Any treatment-emergent serious AEs (TESAEs)
- Any study drug related TESAEs
- Any TEAEs leading to death.

The TEAEs described above will be summarized separately by system organ class and preferred term. The non-serious TEAEs occurring in more than 2% of participants in any treatment group and preferred term will be summarized.

Listings will be presented specifically for TEAEs, TESAEs and TEAEs leading to discontinuation of study drug and TEAEs leading to death.

3.5.2 *Event of Special Interest*

Events of special interest (ESIs) include the following: hepatic abnormalities, muscle-related abnormalities, new-onset diabetes mellitus (NODM) and/or hyperglycemia, renal abnormalities, changes to antihypertensive medication(s) due to changes in blood pressure, and macular degeneration described as follows:

- AST or ALT > 3×ULN;
- Total bilirubin > 2×ULN;
- Creatine kinase (CK) > 5 × ULN;
- NODM or worsening of glycemic control;

Note: NODM is defined by 1 or more of the following criteria, based upon information from AE, medication, and laboratory data:

- AE indicating new type 1 or type 2 diabetes;

- Initiation of anti-diabetes medication with confirmation of the diagnosis of diabetes by blinded external review by experts in diabetology;
- HbA1c $\geq 6.5\%$ (≥ 0.065 hemoglobin fraction); and/or
- Two consecutive values of fasting plasma glucose that are ≥ 126 mg/dL (≥ 7.0 mmol/L).

Note: Worsening of glycemic control will be defined as HbA1c increase from Baseline $>0.5\%$ (>0.005 hemoglobin fraction) and/or a new concomitant medication or increase in current antidiabetic therapy in a participant with a Baseline HbA1c $\geq 6.5\%$ (≥ 0.065 hemoglobin fraction)

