- A $>25\%$ decrease in eGFR from Baseline or an eGFR < 30 mL/min/1.73 m², calculated using the Chronic Kidney Disease Epidemiology Collaboration equation, and/or an increase in serum creatinine of ≥ 0.3 mg/dL (≥ 26.5 μ mol/L) from Baseline;
- Changes to antihypertensive medication(s) due to changes in blood pressure in those participants receiving antihypertensive medication(s) treatment at Baseline and those participants not receiving antihypertensive medication(s) treatment at Baseline; and
- Macular degeneration.

An overview of ESIs described above will be provided including counts, percentages of participants by treatment group, and a listing of each ESI.

Values and changes from baseline will be summarized for ALT, AST, and total bilirubin by visit and treatment group. The number and percent of participants with abnormal values for ALT, AST, and total bilirubin will be summarized. These summaries of participants with abnormal values will be performed overall; by normal Baseline; and by abnormal Baseline for ALT, AST, and total bilirubin individually. Hy's Law criteria ($>3 \times \text{ULN}$ for either ALT or AST, with accompanying total bilirubin $>2 \times \text{ULN}$) will also be applied to the data. Any potential Hy's Law cases will be listed separately.

Values and changes from Baseline will be summarized for CK levels by visit and treatment group and visit. In addition, the number and percent of participants with abnormal CK values will be summarized. These summaries of participants with abnormal CK values will be performed overall, by normal Baseline CK, and by abnormal Baseline CK. Values of CK from Baseline to EOT will be summarized by treatment group and by Baseline eGFR category.

Cases of NODM will be recorded and summarized using the appropriate system organ class. These events will be summarized by severity and relationship to study drug for each treatment group. Fasting plasma glucose and HbA1c will be monitored as specified in [Table 1 Schedule of Procedures](#).

Baseline eGFR will be summarized by treatment group for actual value and for Baseline eGFR categories. Shift tables of eGFR category from Baseline to EOT will be provided by treatment group. Shift tables of urine albumin-creatinine ratio and urine protein-creatinine ratio from Baseline to EOT will be provided by treatment group.

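### NODM cases met only on HbA1c or fasting glucose can lack an AE record and drop out of the only NODM-specific summary, and no separate count by the full definition is specified

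*Protocol*

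**What the plan says.** Protocol 8.1.4 and SAP 3.5.2 give the same definition of NODM: at least one of four criteria, "based upon information from AE, medication, and laboratory data". One criterion is an AE, one is a new anti-diabetes drug with externally confirmed diagnosis, and two are laboratory thresholds (HbA1c; consecutive fasting glucose). Protocol 8.1.4 has the DSMB monitor ESIs "regardless of whether these events were reported as AEs", and adds that those qualifying as AEs are also reported as AEs.

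On laboratory findings, Protocol 8.7.4 tells sites: "In general, laboratory abnormalities without clinical significance should not be recorded as AEs".

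On analysis, Protocol 9.2.2.1 says: "Cases of NODM will be recorded and summarized using the appropriate system organ class. These events will be summarized by severity and relationship". SAP 3.5.2 repeats both sentences. It also promises: "An overview of ESIs described above will be provided including counts, percentages of participants by treatment group, and a listing of each ESI". In the list to which that overview refers, one bullet reads "NODM or worsening of glycemic control".

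**The concern.** The definition admits cases that have no AE, while the planned NODM summary needs attributes that only an AE has. Neither document says how to treat a case that meets the definition without an AE record.

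The other place where NODM is counted is the ESI overview, whose source bullet also covers worsening of existing disease. That matters because participants with diabetes can enrol. Exclusion criterion 7 applies only from HbA1c 10.0% or fasting glucose 270 mg/dL, and SAP 3.4.4 has a diabetes (yes/no) subgroup.

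At stake is the count of a prespecified safety event: incomplete in one table, possibly mixed with something else in the other. Other ESIs are handled more fully. ALT, AST, bilirubin and CK each get the number and percentage of participants with abnormal values, and SAP 3.5.2 gives an explicit derivation rule for antihypertensive changes. NODM, which is partly defined by laboratory values, gets neither.

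**Working it through.** The plan states no figure on this point, so there is none to reproduce. The check traces each criterion to the AE rules and then to the planned outputs.

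**1. Criteria against AE rules**

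| NODM criterion | AE required by definition? | What would create an AE record |
|---|---|---|
| AE of new diabetes | Yes | The criterion itself |
| New anti-diabetes drug, diagnosis confirmed | No | Normally Protocol 8.1 (intervention required) and 8.7.4 (change in concomitant therapy) |
| HbA1c ≥6.5% | No | Only if the investigator considers it clinically significant or action follows |
| Two consecutive fasting glucose ≥126 mg/dL | No | As for HbA1c |

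Three of the four criteria do not require an AE. The medication criterion normally leads to one, which leaves two where a case can realistically have none. An example is a participant who goes from HbA1c 6.4% to 6.5% without symptoms or treatment.

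**2. Attributes needed by the NODM summary.** Protocol 8.1.3 has the investigator rate severity and relationship for each AE. Protocol 9.2.2 and SAP 3.5.1 apply system organ class coding to AEs. An unreported laboratory case has none of the three.

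**3. Other outputs**
- ESI overview: counts and percentages by group, from a list with a combined bullet.
- ESI listing: shows each case, with no count by group.
- SAP 3.5.3 shift tables: low/normal/high at the end of treatment, so neither the NODM thresholds nor earlier visits.
- Change-from-Baseline summaries of HbA1c and glucose: no count of cases.

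**4. Illustration of direction only.** The documents give no rates. Assumed: 200 obicetrapib and 100 placebo (the planned 2:1 split of 300); 20% diabetic at Baseline (40 and 20); NODM by any criterion in 12 and 3 of the others, which is 6% and 3% of each arm; 25% of diabetics worsening in each arm (10 and 5).
- True NODM ratio: (12/200)/(3/100) = 6%/3% = 2.0.
- Overview line if combined: (12+10)/200 = 11.0%; (3+5)/100 = 8.0%; ratio 11.0/8.0 = 1.38. With no worsening the ratio is 2.0. With all diabetics worsening it is (52/200)/(23/100) = 26%/23% = 1.13.
- AE-based table if one third of cases are reported as AEs in both arms: 4/200 against 1/100, 2% against 1%, ratio 2.0. At two thirds: 8/200 against 2/100, 4% against 2%, ratio 2.0. Cases are lost, but with equal reporting in both arms the ratio is not diluted.

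**5. Check on the remedy.** The HbA1c and glucose criteria are not restricted to participants without diabetes at Baseline. If all 40 and 20 assumed diabetics had HbA1c ≥6.5%, a literal count of anyone meeting any criterion would be (12+40)/200 = 26% against (3+20)/100 = 23%, ratio 1.13. Restricted to participants without diabetes at Baseline it is 12/160 = 7.5% against 3/80 = 3.75%, ratio 2.0. The restriction is therefore essential.

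**The case against.** A reader might infer that all three non-AE criteria have no AE record and cannot enter the NODM table. The documents do not support that. Protocol 8.1.4 has qualifying ESIs reported as AEs, and Protocol 8.1 and 8.7.4 normally send a drug-treated case to the AE form. Protocol 8.1 also asks for the specific disease to be recorded, and Protocol 8.1.4.3 has newly diagnosed diabetes referred for education and management, so many laboratory-defined cases would be reported too. What remains are laboratory-only cases that the investigator does not report, and their number is unknown.

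A reader might also infer that the overview will certainly merge NODM with worsening. The bullet is combined, but the two are defined in separate notes, and SAP 3.5.2 does not rule out separate lines. The detailed programming specifications are a separate document.

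Nor would a signal be invisible. HbA1c and fasting glucose are in both chemistry panels (Protocol Appendix B), each ESI is listed, and the DSMB reviews unblinded ESIs. Even the full assumed count gives only z = 0.03/√(0.06×0.94/200 + 0.03×0.97/100) = 0.03/0.0239 ≈ 1.25, and safety analysis is descriptive.

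All of this stands and limits the point. It does not supply a rule for the unreported laboratory case or a count of NODM as the documents define it. A descriptive safety table still has to count what it claims to count.

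**Conclusion.** The mismatch is in the current text of both documents. NODM cases met only on HbA1c or consecutive fasting glucose do not require an AE, and those not reported as AEs drop out of the only NODM-specific summary. Because no separate count by the full definition is specified and the overview follows a combined bullet, new-onset cases may be undercounted in one table and mixed with worsening of known diabetes in the other.

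The size cannot be derived from the documents. It depends on how many laboratory-only cases go unreported, how many participants have diabetes at Baseline, and whether the overview is split. The figures above show direction under assumed rates and predict nothing. The stronger conclusion, that an excess of diabetes on obicetrapib would be hidden, is not supported, since listings and laboratory summaries show the underlying data and the AE-based table keeps the relative excess if reporting is equal between arms. This is a modest reporting gap that is worth closing because the better count uses data already collected.

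**What to change.** In Protocol 9.2.2.1 and SAP 3.5.2, replace the NODM summary with:

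> Among participants without diabetes at Baseline, NODM will be summarized by treatment group as the number and percentage meeting any criterion, and by criterion (AE; medication with confirmed diagnosis; HbA1c; fasting glucose). Severity and relationship will be summarized only for NODM reported as an AE. NODM and worsening of glycemic control will be shown on separate lines in the ESI overview.

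Define diabetes at Baseline as for the SAP's diabetes (yes/no) subgroup, which SAP 3.3.4 and 3.4.4 list without stating a rule. Reconcile it with the Baseline HbA1c ≥6.5% condition in the worsening definition, so that a participant with known diabetes and a Baseline HbA1c below 6.5% is classified unambiguously.

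The cost is SAP wording, the matching protocol sentence and one small table. No new data are needed.
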